Pump factors - CR, ISF, and AIT ^b	All patients in the Randomized Population with a baseline and at least one post-baseline observation	Last value of Visits 2-4 prior to or on the date of the first dose of IP	Last observation 1 day prior to Visit 7 and last observation 1 day prior to Visit 10 prior to last dose in IP of each randomized treatment period (Period I and Period II) excluding data (if any) that are collected while patients temporarily are off pump or off IP

Baseline and Post-Baseline Definitions and Patient Population by Study Period and Type of Analysis

Study Period/Analysis	Patient Population	Baseline Observations	Post-Baseline Observations
4-Week of Each Randomized Treatment Period Regardless of IP use (from randomization to Week 4 of each randomized treatment period regardless of IP use)			
TEAEs	Randomized Population	Prior to first dose of randomized IP (or Visit 4 if the dose date is missing)	Each 4-week randomized treatment period regardless of IP use
Weight and vital signs	All patients in the Randomized Population with a baseline and a post-baseline observation	Last of Visits 2-4	Visits 7 and 10 regardless of IP use
Week 2-4 of Each Randomized Treatment Period while on IP			
CGM outcome variables	All patients in the Randomized Population (with a baseline and a post-baseline observation for continuous variables, unless otherwise specified ^c)	From first to last dose of open-label Humalog, excluding data (if any) that are collected while patients temporarily are off pump or off open-label Humalog	From first to last dose of IP in each randomized treatment period (Period I and Period II), excluding data (if any) that are collected while patients temporarily are off pump or off IP
Week 2-4 of Each Randomized Treatment Period Regardless of IP			
Basal, bolus, and total insulin doses, bolus/total insulin dose ratios ^d	All patients in the Randomized Population with a baseline and a post-baseline observation	Last of Visits 2-4	Visits 7 and 10 regardless of IP use
Basal, bolus, and total insulin doses, bolus/total insulin dose ratios by infusion set wear day, by meal, and by infusion set wear day and meal ^e	All patients in the Randomized Population with a baseline and a post-baseline observation	Last of Visits 2-4	Last observed value before/at Visit 7 and before/at Visit 10 regardless of IP use

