Percentage of time (per week) spent in Auto Mode ^f	All patients in the Randomized Population with a baseline and a post-baseline observation	Last of Visits 2-4	Visits 7 and 10 regardless of IP use
Safety Follow-Up Visit (Overall^a Only)			
TEAEs	All patients in the Randomized Population who enter the safety follow-up period	Prior to first dose of randomized IP (or Visit 4 if the dose date is missing)	From the date of the last visit of the 8-Week treatment period + 1 day to the end of study
Weight and vital signs	All patients in the Randomized Population who enter the safety follow-up period	Last of Visits 2-4	Visit 801

Abbreviations: 1,5-AG = 1,5-Anhydroglucitol; AIT = active insulin time; BG = blood glucose; CGM = continuous glucose monitoring; CR = carb ratio; eCRFs = electronic case report forms; HbA1c = hemoglobin A1c; IP = investigational product; ISF = insulin sensitivity factor; TEAE = treatment-emergent adverse event.

- a “Overall” means that data will be summarized in total and no by-treatment summary or statistical analysis will be included.
- b The pump settings that patients started with in each treatment period (lead-in, Period I and Period II) are captured in the eCRF. Changes during the study are captured in CareLink raw data. The pump settings that patients ended up within each treatment period will be the last observed value from the two data sources 1 day prior to the last office visit.
- c Not required for the duration of hypoglycemic episode because it is possible that some patients may not have any hypoglycemic event during the lead-in period to be used as baseline values.
- d Mean insulin doses (mean total daily basal and mean total daily bolus) during the last 1 week for Visit 2 and during the last 2 weeks for Visits 4, 7, and 10 from the CareLink report will be entered into eCRFs. These data will be used for summary and analyses of mean total daily basal dose, mean total daily bolus dose, mean total daily insulin dose, and the ratio of mean total daily bolus dose to mean total daily insulin dose.
- e Calculated from the CareLink raw data by adding up all insulin doses that fall into the specified time interval (e.g., a specific infusion set wear day), regardless of whether the pump is in Auto Mode or not.
- f Captured in the eCRF as “percentage of time spent in Auto Mode per week for the past 1 week” at Visit 2 and as “percentage of time spent in Auto Mode per week for the past 2 weeks” at other visits.

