6.9.2. Other Secondary Efficacy Analyses

The analyses described in Section 6.9.2 will include data collected from the Randomized Population. Details for the CGM analyses are described in Section 6.13.

For the following secondary efficacy endpoints during the last 2 weeks of each 4-week treatment period, an MMRM model similar to that for the primary endpoint will be used:

- actual and change from baseline in insulin doses, including mean total daily basal (U/day, U/kg/day), mean total daily bolus (U/day, U/kg/day), and mean total daily insulin dose (U/day, U/kg/day) and mean total daily bolus /mean total daily insulin dose ratios (%)
- actual and change from baseline in percentage of time (per week) spent in Auto Mode, during the last 2 weeks of each 4-week treatment period
- actual and change from baseline in percentage of time with sensor glucose values <54 mg/dL as measured by CGM

In addition, the longitudinal observations of actual and change during each 4-week treatment period in HbA1c and 1,5-AG will be summarized by period and by treatment sequence. No treatment comparison will be conducted.

To assess the insulin doses over the course of 3 days of continuous infusion, the mean total daily basal and mean total bolus doses during the last 2 weeks of the lead-in and each 4-week treatment period, will be derived based upon the CareLink raw data collected on Day 1, Day 2, and Day 3 of infusion set wear and summarized by treatment. The insulin doses will also be summarized by infusion set wear day, and by both infusion set wear day and meal (0 to 4 hours after the start of meals, excluding data collected after the next meal for the current meal). Only data from the infusion sets with ≥ 60 hours of wear will be included in these doses analyses by infusion set wear day. The treatment comparison will be conducted using an MMRM model similar to that for the primary endpoint.

Before the database lock, it was identified that 1 patient had to replace the pump in the middle of the study and Auto Mode was unavailable for at least 48 hours, and thus data from this patient will be excluded from analysis of percentage of time (per week) spent in Auto Mode.

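### Insulin doses by infusion set wear day are 2-week means in SAP 6.9.2 but a last observed value in SAP Table ITSM.6.2, and nothing says which rule governs

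*SAP*

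**What the plan says.** SAP 6.9.2 describes an analysis of dosing over the life of an infusion set. The quantities are "the mean total daily basal and mean total bolus doses during the last 2 weeks of the lead-in and each 4-week treatment period", to be "derived based upon the CareLink raw data collected on Day 1, Day 2, and Day 3 of infusion set wear and summarized by treatment". It adds: "The insulin doses will also be summarized by infusion set wear day, and by both infusion set wear day and meal". Only sets worn at least 60 hours count, and treatments are compared with an MMRM like that for the primary endpoint.

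SAP Table ITSM.6.2 (Section 6.1) has a row for basal, bolus and total doses and "bolus/total insulin dose ratios by infusion set wear day, by meal, and by infusion set wear day and meal". It stands under the block heading "Week 2-4 of Each Randomized Treatment Period Regardless of IP". Its baseline is "Last of Visits 2-4" and its post-baseline observation is "Last observed value before/at Visit 7 and before/at Visit 10 regardless of IP use". Footnote e, attached to this row, reads in part: "Calculated from the CareLink raw data by adding up all insulin doses that fall into the specified time interval". One wear day is its example of an interval. The footnote does not say how repeated intervals in the window are combined.

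The SAP revision history lists a baseline and post-baseline definition for doses by wear day among the version 3 additions, so the row is deliberate current text.

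**The concern.** Two places in the SAP define the observation for the same treatment comparison, and they define it differently. A programmer following 6.9.2 averages every eligible Day 1 (or Day 2, or Day 3) in the window. A programmer following the table could take the most recent such day and stop. The two datasets would give different estimates and interval widths, and the choice would be made outside the plan.

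Under the literal table rule, the set that supplies the value also depends on visit timing. Protocol 7.2 and the Schedule of Activities have the infusion set changed at the site at Visits 7 and 10. The set in use at the visit may therefore be cut short and fail the 60-hour filter, so that an earlier set supplies the value.

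The baseline differs too. SAP 6.9.2 uses the lead-in, while the table allows a fallback to Visit 2, the visit at which open-label Humalog starts. Before it, a patient may have been using insulin aspart (Protocol 6.1, criterion 6).

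**Working it through.** The plan gives no figure of its own on this point. The check compares the wording, counts the sets and illustrates the loss of precision.

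**1. What the wording supports**
- The ordinary daily-dose and Auto Mode rows name Visits 7 and 10, and footnotes d and f supply the 2-week window. The wear-day row has no such footnote.
- For pump settings, footnote b uses the same last-observed wording for a single final record.
- The block heading above the row restricts the data to Weeks 2 to 4, which fits either reading.

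**2. How many sets each rule uses**

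Inputs: a 14-day window (SAP 6.9.2), a set change every 3 days (SAP 5.3) and the 60-hour minimum (SAP 6.1 and 6.9.2).

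Nominal count: 14/3 = 4.67 sets.

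Take a 28-day period with changes on days 0, 3, ..., 27 and a window of days 14 to 28. The set started on day 27 is worn for 1 day and fails the filter.
- Day 1 of wear comes from the sets started on days 15, 18, 21 and 24: 4 values.
- Day 2 comes from the same sets: 4 values.
- Day 3 comes from those sets plus the set started on day 12: 5 values.

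Periods of 25, 27, 29 and 31 days, within the 3-day visit window, also give 4 or 5 values per wear day. The literal table rule gives 1.

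**3. What that does to precision (assumed SDs)**

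Let s_w be the set-to-set SD within a patient and period, s_b the patient-by-period SD, and k the number of sets averaged. The patient's own level cancels in the crossover difference, so

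SD of the between-period difference = √(2(s_w²/k + s_b²)).

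| s_w, s_b (U) | k = 1 | k = 14/3 | Ratio |
|---|---|---|---|
| 9, 3 | √(2(81 + 9)) = 13.4 | √(2(17.36 + 9)) = 7.3 | 1.85 |
| 7, 3 | √(2(49 + 9)) = 10.8 | √(2(10.5 + 9)) = 6.2 | 1.72 |
| 9, 5 | √(2(81 + 25)) = 14.6 | √(2(17.36 + 25)) = 9.2 | 1.58 |
| 7, 5 | √(2(49 + 25)) = 12.2 | √(2(10.5 + 25)) = 8.4 | 1.44 |
| equal | – | – | √(2/(3/14 + 1)) = 1.28 |
| 7, 9 | √(2(49 + 81)) = 16.1 | √(2(10.5 + 81)) = 13.5 | 1.19 |

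With k = 4, the lower count after the filter, the first and last rows become √(90/29.25) = 1.75 and √(130/93.25) = 1.18. Under this model the ratio for k = 14/3 always lies between 1 (s_w negligible) and √(14/3) = 2.16 (s_b negligible).

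**4. Doses by meal alone**

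These are in the table row but not in the 6.9.2 sentences on wear day. Read literally, the table would take one meal occasion, against about 14 for a given daily meal in 2 weeks. SAP 6.9.2 states no 2-week mean for this breakdown, so here the gap is a missing rule and not a contradiction.

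**The case against.** The best defence is that the passages can be read together. The row sits under a Week 2 to 4 heading and 6.9.2 gives the derivation, so the table may only select which derived record enters the model. The CGM row works in a similar way: its cell runs from first to last dose under the same kind of heading, and SAP 6.13 supplies the 2-to-4-week derivation. Footnote e is silent on averaging; it does not exclude it. This reading is possible, so the documents do not establish that one set will be used. The defect remains, because the SAP does not state this reading and footnote b uses similar wording for a single record.

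A reader might also infer that visit-based baselines cannot exist for raw-data doses. That goes too far. The SAP labels multi-day raw-data aggregates by visit: the example in its Section 9.2 assigns 3078 readings, about 3078/288 = 10.7 days, to Visit 7. What is missing is a definition of the window behind the visit label, and the label does not match the lead-in window in 6.9.2.

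Finally, these doses are not a listed objective. Objective 7 concerns mean total daily bolus and basal dose, which footnote d defines as 2-week means entered in the eCRF. That limit on importance stands in full.

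**Conclusion.** The inconsistency is real and should be corrected, but its reach is small. For doses by wear day, and by wear day and meal, SAP 6.9.2 and Table ITSM.6.2 as written define different observations for an MMRM treatment comparison. The literal table rule uses 1 set per wear day against 4 to 5, with a baseline that does not match the lead-in.

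The direction of the precision loss is clear; its size is not. A reader might take the upper part of the table above and conclude that confidence intervals would be 1.4 to 1.85 times wider. The documents do not support that: they give no variance components, and those ratios arise only where set-to-set variation is assumed to exceed patient-by-period variation. Across all the assumed pairs the range is roughly 1.2 to 1.85. One pair of SDs in units also cannot represent basal, bolus, total and per-meal doses and the ratios, all of which share this row.

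The baseline mismatch matters mainly for change-from-baseline summaries. A patient's baseline is common to both periods and largely cancels in the within-patient comparison.

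The wear-day and meal dose analyses in SAP 6.9.2 and their bolus-speed version in SAP 6.14 are affected. The primary endpoint and the eCRF-based mean daily doses are not.

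**What to change.** Rewrite the Table ITSM.6.2 row, keeping CareLink raw data as the source and the inclusion of data regardless of IP use:
- **Baseline:** the mean over the 2-week lead-in.
- **Post-baseline:** the mean over the last 2 weeks of each treatment period.
- **By wear day, and by wear day and meal:** average over infusion sets worn at least 60 hours.
- **By meal alone:** average over all meal occasions in the window, without the 60-hour filter, which the SAP applies only to wear-day analyses.

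Add to footnote e that interval sums are averaged over the repeated intervals in the window. The cost is one row and one sentence, with no new data, since 6.9.2 already describes the wear-day derivation. SAP 6.1 allows a change of this kind, with its justification, to be recorded in the SAP or the clinical study report.

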10.3.4. Safety Analyses

Safety measures will include AEs, hypoglycemia, vital signs, treatment exposure, and laboratory measures.

Events that are newly reported after the first dose of rapid-acting insulin provided as study drug (i.e., open-label Humalog used during the lead-in period or IP used during each of the two 4-week randomized treatment periods) or reported to worsen in severity from baseline (details will be described in SAP) will be considered -TEAEs. Events that continue during more than 1 study period (lead-in, Period I, and Period II) with the same severity will only be counted once for the first study period.

Serious AEs, AEs reported as reason for discontinuation from the IP or study, and TEAEs will be summarized in tables using the Medical Dictionary for Regulatory Activities (MedDRA) PT, sorted by decreasing frequency within the LY900014 treated-patients. Treatment-emergent AEs

will also be summarized by PT sorted by decreasing frequency within SOC for all TEAEs and by maximum severity. For events that are gender-specific (as defined by MedDRA), the denominator and computation of the percentage will include only patients from the given gender. The number and proportion of patients with at least 1 event for each type of event will be summarized and compared between treatments using Prescott's exact test.

Hypoglycemia rates will be summarized for periods of 1 year, and 100 years (severe hypoglycemia only) for both treatment periods. Wilcoxon Signed-Rank test and Prescott's exact test will be used instead to analyze the rate and incidence of hypoglycemia events, respectively.

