6.1. General Considerations

Statistical analysis of this study will be the responsibility of Lilly or its designee. Any change to the data analysis methods described in the protocol will require an amendment ONLY if it changes a principal feature of the protocol. Any other change to the data analysis methods described in the protocol, and the justification for making the change, will be described in the SAP or the clinical study report (CSR). Additional exploratory analyses of data will be conducted, as deemed appropriate.

For purposes of analysis, the following populations are defined in [Table ITSM.6.1](#):

Table ITSM.6.1. Patient Populations

Population	Description
Entered	All patients who give informed consent.
Enrolled	All patients who receive at least 1 dose of open-label Humalog in the 2-week lead-in period.
Randomized	All patients who are randomly assigned to study treatment at Visit 4 and receive at least 1 dose of the randomly assigned IP. Treatment will be defined on the basis of the treatment the patients are assigned to.
Pilot	All patients in the pilot safety assessment.

Unless otherwise specified, all efficacy and safety analyses will be conducted on the Randomized Population. Analyses of adverse events (AEs) will include all data collected during the course of the entire 4-week treatment period for each treatment regardless of IP use. Analyses of hypoglycemia and CGM measures will be conducted using the data from first dose to last dose of IP in each 4-week treatment period, and due to the crossover design, treatment comparisons will be based upon the derived outcome variables for Week 2 to 4 in each 4-week treatment period. Analyses of the CareLink report data that are transferred to eCRF (eg, percentage of time spent in Auto Mode, total daily doses during the last 2 weeks) will include all data collected, regardless if patients are temporarily off pump or IP during the 2 weeks or not. Pump-related safety analyses (eg, infusion set changes) will exclude data (if any) that are collected while patients are temporarily off pump or off IP. For analyses of CGM, insulin doses and meal information by infusion set wear day, only data from the infusion sets with ≥ 60 hours (2.5 days) of wear will be included so that adequate data can be used for by-day (Day 1, Day 2, and Day 3) comparison. Data collected during the safety follow-up period will not be used for comparisons between treatments.

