6.10.2. Adverse Events

Events that are newly reported after the first dose of rapid-acting insulin provided as study drug (ie, open-label Humalog used during the lead-in period or IP used during each of the two 4-week randomized treatment periods) or are reported to worsen in severity from baseline (defined in [Table ITSM.6.2](#) for each specific study period) will be considered treatment-emergent adverse events (TEAEs). Events that continue during more than 1 study period (lead-in, Period I, Period II) with the same severity will only be counted once for the first study period.

The MedDRA Lowest Level Term (LLT) will be used in the treatment-emergent assessment. The maximum severity for each LLT during the baseline period will be used as baseline severity. For events occurring on the day of first dose of blinded insulin provided in this study during each treatment period (lead-in, Period I and Period II), the CRF-collected flag will be used to determine whether the event started or worsened post-treatment, and/or the treatment of which period the AE should be assigned.

In an overview table, the number and percentage of patients who experienced a TEAE, experienced a serious adverse event (SAE), died due to an AE, and discontinued from study due to an AE will be summarized.

The number and percentage of patients with SAEs and who discontinued from the study due to an AE will be summarized using MedDRA PT nested within SOC if any such events occurred. Prescott's exact test will be performed for treatment comparison. The number and percentage of patients with TEAEs will be summarized by treatment using MedDRA PT nested within SOC. Events will be ordered by decreasing frequency within SOC. As an additional table, the percentages of patients with TEAEs will be summarized by treatment using MedDRA PT (without regard to SOC). Events will be ordered by decreasing frequency in total group. Statistical comparisons will be applied at both the SOC and PT levels. Prescott's exact test will be performed for treatment comparison.

The number and percentage of patients with TEAEs by maximum severity will be summarized by treatment using MedDRA PT nested within SOC. For each patient and TEAE on each treatment, the maximum severity for the MedDRA PT is the maximum postbaseline severity

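### As worded, the SAP can count an adverse event that first appeared or worsened on randomized insulin, and merely continues after the last treatment visit, again as emergent in the overall safety follow-up table.

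*SAP*

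**What the plan says.** The follow-up TEAE row of Table ITSM.6.2 (SAP 6.1) gives as baseline "Prior to first dose of randomized IP (or Visit 4 if the dose date is missing"), the same wording as the randomized-treatment TEAE row. Its post-baseline window is "From the date of the last visit of the 8-Week treatment period + 1 day to the end of study".

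SAP 6.10.2 calls an event treatment-emergent if it is newly reported after the first dose of study insulin, or "reported to worsen in severity from baseline (defined in" Table ITSM.6.2 for each specific study period). It also states: "The maximum severity for each LLT during the baseline period will be used as baseline severity".

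The one stated rule against repeat counting is "Events that continue during more than 1 study period (lead-in, Period I, Period II) with the same severity will only be counted once". Protocol 10.3.4 has the same rule with the same three periods: "Events that continue during more than 1 study period (lead-in, Period I, and Period II) with the same severity will only be counted once". Neither document names the safety follow-up.

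On use of the data, the footnote to the word Overall says that it "means that data will be summarized in total and no by-treatment summary or statistical analysis will be included". SAP 6.1 adds: "Data collected during the safety follow-up period will not be used for comparisons between treatments". Table ITSM.6.3 plans a single analysis for follow-up, TEAEs by preferred term.

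**The concern.** A follow-up TEAE table is normally read as showing what appears or worsens after investigational product (IP) stops and patients return to nonstudy insulin. Here the baseline closes at the first randomized dose and the window opens after the last treatment visit, so about 8 weeks on IP inform neither side. An event that began in that gap has no baseline severity. If it is still present in follow-up, it can meet the TEAE definition there even though it is unchanged or improving and was already counted under LY900014 or Humalog.

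At stake is the meaning of one planned safety table. Ongoing on-treatment events and events arising off IP would be mixed under the same preferred terms, and the table itself gives no means of telling them apart.

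**Working it through.** The plan states no figure on this point, so the check applies its rules to test events.

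**Rules used**
1. Follow-up baseline: before the first randomized dose (Table ITSM.6.2).
2. Follow-up window: from the day after the last treatment-period visit (Table ITSM.6.2).
3. Emergent means new, or worse than the maximum baseline severity for that Lowest Level Term, LLT (SAP 6.10.2).
4. Count-once: lead-in, Period I and Period II, same severity (SAP 6.10.2).

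The test assumes that an event enters the follow-up table by being present in the window; the SAP does not say whether presence or onset decides.

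**Counts in the follow-up table**

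| Test event (before randomization / on IP / follow-up) | As written | Count-once extended | Baseline moved to last treatment visit |
|---|---|---|---|
| none / mild / still mild | 1 | 0 | 0 |
| none / moderate / continuing, now mild | 1 | 0 | 0 |
| mild / moderate / still moderate | 1 | 0 | 0 |
| mild / moderate / continuing, back to mild | 0 | 0 | 0 |
| mild / mild / mild | 0 | 0 | 0 |
| none / none / first appears | 1 | 1 | 1 |
| none / mild / continuing, now moderate | 1 | 1 | 1 |
| none / mild, resolved / separate new mild episode | 1 | 1 | 0 |

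The first three events are already TEAEs in the treatment-period table, so each appears in two tables. Rows four and five show that the existing baseline does screen out events no worse than before randomization. The last row is where the two possible corrections differ.

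**Comparison with the other periods.** In the lead-in row, baseline and window meet at the first open-label dose. Periods I and II share one baseline, but a mild event running from Period I into Period II at the same severity is removed from Period II by the count-once rule. The follow-up row has neither an adjoining baseline nor that rule.

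**Size.** The documents give no adverse event rates and no number of events ongoing at Visit 10. An illustration on assumed rates shows how little can be said. SAP 5.2 gives 42 × (1 − 0.12) = 37 completers. Assume that a share p of 30% to 60% have a TEAE in 8 weeks, and that 15% to 30% of those are ongoing at the end.

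- Re-counted patients: 37 × 0.30 × 0.15 = 1.7; 37 × 0.30 × 0.30 = 3.3; 37 × 0.60 × 0.15 = 3.3; 37 × 0.60 × 0.30 = 6.7.
- Patients with a new event in 2 weeks at a constant rate, 37 × (1 − (1 − p)^(2/8)): 3.2 for p = 0.30 and 7.6 for p = 0.60.
- Ratio of re-counted to new, from unrounded counts: 0.53 and 1.05 for p = 0.30; 0.44 and 0.88 for p = 0.60.

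The ratio runs from about 0.44 to 1.05 on assumptions alone. The two groups can overlap, and patients who stop early also go into safety follow-up, so this is not an estimate.

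**The case against.** The strongest reply is that the SAP never says an event enters the follow-up table by presence. If the programmers require onset or worsening inside the window, an unchanged Period II event is not counted again. SAP 6.10.2 gives this some support: for events on the day of first dose, a CRF flag decides whether the event started or worsened after treatment and to which period it belongs. That rule covers dosing days only. A rule for events continuing across periods would also be largely redundant if only onset mattered. So the repeat count is conditional, but on the more natural reading; at the least, two programmers could produce different tables.

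A second reply is that a pre-randomization baseline fits Protocol Appendix 1, which defines a TEAE against the pretreatment state, and that the follow-up row for weight and vital signs also uses a pretreatment baseline. This stands as a defence of the baseline itself. It does not explain why the count-once rule stops at Period II, and it favors correcting that rule and leaving the baseline alone.

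A third reply is that the events can be separated in patient-level data. SAP 6.10.2 plans a listing of all SAEs including follow-up, and SAP 6.10.7.4 refers to AE listings. That is fair: the ambiguity lies in the summary table, not in everything a reader may consult.

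A reader might also infer an error from the Version 2 entry in the SAP revision history, which describes a different follow-up baseline. That entry records superseded text and is not used here.

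**Conclusion.** The point holds on the current wording, given counting by presence. An event that first appeared or worsened on IP, and continues at the same or a lower severity that is still above its pre-randomization level, is counted again as emergent in follow-up, and no stated rule removes it.

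Three stronger inferences are not supported.
- That follow-up has no protection at all: events already present before randomization at that severity are screened out by the baseline.
- That the follow-up count is inflated by a particular percentage: the documents supply no rates, and the illustration above only reflects its assumptions.
- That the comparison of LY900014 with Humalog is distorted: the follow-up table is overall only, and the by-treatment TEAE tables, the primary analysis and every planned test are unaffected.

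The consequence is therefore small and contained: one descriptive safety table whose content is ambiguous.

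**What to change.** In SAP 6.10.2, extend the list in the count-once rule to *lead-in, Period I, Period II, and safety follow-up*, and state that an event continuing into follow-up at the same or lower severity is not counted there. Only events that start or worsen after the last treatment-period visit are then follow-up-emergent. Word the lower-severity clause for the step into follow-up only; applied between Periods I and II as well, it could change the by-treatment tables, which is a separate decision.

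The cost is one phrase in the SAP and one condition in the AE program. Protocol 10.3.1 allows such a change to be described in the SAP or clinical study report, since it alters no principal feature of the protocol.

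An alternative is to end the follow-up baseline at the last visit of the 8-week treatment period (Visit 10 or early termination), so that it meets the window. Ending it at the last dose instead would leave a gap for events starting between last dose and last visit. The small downside of this alternative is that a separate new episode of the same LLT, at the same or any lower severity after IP stops, would drop out of the follow-up table. Extending the count-once rule avoids that and is preferable.
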